#### **4.4 Sample size calculation**

We aim to enrol a convenience sample of 60 patients in this feasibility study, with n=30 per study group (i.e. plant-based vs animal-based ONS) which is deemed sufficient to answer the primary research question (21, 22).

If the results of this study show that the intervention can be considered feasible, future research with a fully powered sample size shall be performed to investigate the effect of the intervention on all parameters.

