#### **8.1.2 Secondary study parameters/endpoints (if applicable)**

The secondary endpoints of this study is the energy and protein intake, nutritional status, muscle status, physical and clinical outcomes, and patient's satisfaction with long-term supplementation.

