### 8.3 Study procedures

Measurements during this study will be combined as best as possible during appointments planned within routine care at the hospital. Baseline measurements will take place at the start of the ONS treatment (T0) during hospital admission or during an appointment at the outpatient clinic. 1 month after the start (T1) and 2 months after the start (T2) the researcher will have a brief 'check-in' via a phone call or a conversation at the hospital if the patient is there for another appointment. 3 months after initiation (T3) the same measurements will be performed as at baseline (T0). In addition, at T3, the researcher will conduct an interview about patients' satisfaction about the ONS (Table 1).

Table 1: Overview of the study measurements for each time point.

Measurements	Treatment initiation (T0)	1 month after initiation (T1)	2 months after initiation (T2)	3 months after initiation (T3)
Body height, body weight, usual body weight, BMI	X	X	X	X
Nutritional intake (protein and energy)	X			X
Compliance ONS	X	X	X	X
Check-in conversation		X	X	
Nutritional status (PG-SGA, fat mass and fat-free mass, and muscle thickness)	X			X

Hand grip strength	X			X
Physical Activity (SQUASH)	X			X
Physical performance (TUG, SPPB)	X			X
Quality of life (EORTC-QoL-C30) and Clinical outcome measures (length of hospital stay, complications, readmission and mortality)	X			X
Patient's satisfaction about the Oral nutritional supplements				X

Body height, body weight, BMI are measured on a calibrated scale and stadiometer. Usual body weight will be asked. During the check-in process, patients are required to weigh themselves either at home or at the hospital, if they have another appointment scheduled there.

Nutritional intake and compliance of oral nutritional supplements used during hospital admittance will be measured by food registration in the Electronic Patient Record (EPR) registered by the nutritional assistant with a cross-check of a nutritional researcher.

Additionally, the researcher will also ask if there are any variations in their food intake on bad versus good days and whether there have been any changes in eating habits compared to a month ago. Patients who are not admitted to hospital but come to the hospital on an outpatient basis, are being asked to fill out a 3-day food diary (2 week days and 1 weekend day). After 3 months the all patients will all fill out a 3-day food diary. During the 3 months,

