participants will keep a logbook which they must record how much ONS was consumed daily for the total study period.

Individual protein requirement will be set at 1.5-1.9 g/kg FFM and energy requirements at WHO formula + surcharge up to 50% according to the Dutch guidelines of malnutrition and the ESPEN guidelines Clinical nutrition in surgery and cancer (6, 13, 23, 24).

For the check-in conversations the researcher will either make a phone call or have brief conversation at the hospital if the patient is already there for another appointment. The researcher will ask about any changes in body weight, discuss changes in the nutritional advice provided by the dietitian, their satisfaction about the ONS, ensure the patient is still correctly filling out the logbook, and address any questions or concerns related to the study.

Nutritional status will be measured by the Scored Patient-Generated Subjective Global Assessment (PG-SGA). The full PG-SGA has been validated among different patient groups and reported to be a simple instrument to use. Since the PG-SGA consists of a patient-reported part, the Dutch version of the PG-SGA will be used. This version is already available and considered comprehensible and easy to complete by patients, and comprehensible and relevant by professionals (20). One part is completed by the patient and another part by a specialist.

Body composition Fat mass (FM) and fat-free mass (FFM) will be measured using bioelectrical impedance analysis (BIA). The BIA device measures resistance in the body to an alternating current at 50kHz. FFM is then calculated with a formula that includes resistance, height, weight, sex and age. BIA represents a simple, non-invasive measure that takes only 5-10 min to perform.

Muscle thickness will be measured by muscle ultrasound with the Lumify (Philips) at the m. rectus femoris, vastus intermedius and m. biceps brachii.

Handgrip strength will be measured with the JAMAR handheld dynamometer in a standardized manner. Participants are asked to sit in an upward position with their elbows in a 90-degree angle and the wrist in a neutral position (thumb side upwards) and squeeze as hard as possible. Both hands will be measured 3 times, the highest value is used. Handgrip strength is a valid non-invasive method to measure muscle functionality and serves as a predictor for the overall muscle strength and change in nutritional status of participants.

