Physical activity will be assessed using the questionnaire Short QUstionnaire to Assess Health-enhancing physical activity (SQUASH) at baseline and 3 months.

To measure Physical performance, the Short Physical Performance Battery (SPPB) and Timed Up and Go (TUG) will be used. The SPPB combines 3 separate tests, measuring gait speed, standing balance, and ability to rise from a chair. For the SPPB the scores of the 3 sub tests are all converted to a score range of 0-4, making the maximum score 12 points, indicating the best physical function (25). The TUG measures the time it takes for the patient to rise from a chair, walk comfortably 3 meters, turn around, walk back, and sit down. The patient may use their own walking aid and/or orthosis, but no physical assistance or encouragement should be given. This measurement is considered to be a reliable, cost-effective, safe, and time-efficient way to evaluate overall physical performance (26). The TUG and SPPB will be performed at baseline and 3 months.

Quality of Life will be evaluated using the EORTC-QoL-C30, a validated questionnaire for measuring quality of life. Questionnaires will be scored according to the procedures specified by the EORTC-QoL-C30 scoring manual (27).

Clinical outcome measures such as length of hospital stay, mortality and re-admissions within 3 months after hospital discharge will be determined retrospectively by using information from the EPR and confirmed by questionnaire with the participant since admissions from hospitals outside this study are not registered in an EPR. Complications within 3 months after hospital discharge will be determined by using information from the EPR. A complication is defined in line with the Dutch Association of Medical Specialists (FMS) as an unintended and undesirable event or condition during or following medical specialist intervention, which is so harmful to the health of the participant that change in medical treatment is necessary or that there is irreversible damage. Complications will be obtained from patients' medical records during hospital stay up to 3 months after baseline and coded as infectious, decubitus, surgical (non-infectious) complications and other (e.g., cardiopulmonary).

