## **9.2 AEs, SAEs**

### **9.2.1 Adverse events (AEs)**

Adverse events are defined as any undesirable experience occurring to a participant during the study, whether or not considered related to oral nutritional supplements intervention or study procedures. All adverse events reported spontaneously by the participant or observed by the investigator or his staff will be recorded.

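### Complications are taken from the hospital record alone, although the protocol says that record does not show outside admissions and adds participant confirmation for the other clinical outcomes

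*Protocol*

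**What the plan says.** Clinical outcomes are among the secondary endpoints in Protocol Section 8.1.2 ("nutritional status, muscle status, physical and clinical outcomes, and patient's satisfaction with long-term supplementation"). Table 1 in Section 8.3 lists them in one row, marked at T0 and T3: "Clinical outcome measures (length of hospital stay, complications, readmission and mortality").

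The clinical outcomes paragraph of Section 8.3 then sets the data sources. Length of stay, mortality and re-admissions come from the EPR and are "confirmed by questionnaire with the participant since admissions from hospitals outside this study are not registered in an EPR". For complications the text is: "Complications within 3 months after hospital discharge will be determined by using information from the EPR". After defining a complication, the paragraph returns to the source and gives a different window: "Complications will be obtained from patients' medical records during hospital stay up to 3 months after baseline". Complications are coded into four categories: infectious, decubitus, non-infectious surgical, and other.

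**The concern.** The protocol identifies a gap in its own data source, closes it for three of the four clinical outcomes in the Table 1 row, and leaves it open for the fourth without giving a reason. If an outside admission does not appear in the study hospital's record, the complication that led to it need not appear there either.

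Two things are at stake. The complication count would be too low. It could also contradict the re-admission count: a participant admitted to a regional hospital with pneumonia would be a re-admission through the questionnaire but could have no infectious complication on file. Secondary research question 2 in Section 2 asks how clinical outcomes differ between the two products, so the complication outcome should be recorded as completely as the outcomes reported beside it.

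**Working it through.** No arithmetic is involved in the main point. No error rate, power, effect size or sample size depends on it, and the 60 patients are a convenience sample without a formula (Section 4.4: "We aim to enrol a convenience sample of 60 patients in this feasibility study, with n=30 per study group"). The check is a comparison of the text.

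**Step 1: sources by outcome (Section 8.3).**
- Length of stay, mortality, re-admissions: EPR plus participant questionnaire.
- Complications, first statement: EPR.
- Complications, second statement: medical records.

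Neither statement on complications mentions the participant or records from other hospitals.

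**Step 2: could another part of the protocol supply the missing source?**
- T1 and T2 check-ins (Section 8.3): "The researcher will ask about any changes in body weight, discuss changes in the nutritional advice provided by the dietitian". The remaining topics are satisfaction with the supplement, the logbook, and questions or concerns about the study. Complications and outside care are not among them.
- Adverse events (Section 9.2.1): "All adverse events reported spontaneously by the participant or observed by the investigator or his staff will be recorded". This is passive reporting, and nothing links it to the complication outcome.
- Serious adverse events (Section 9.2.2): life-threatening events and new or prolonged hospitalisation are exempt from the investigator's reporting to the sponsor, so an outside admission need not surface by that route.
- Data handling (Section 12.1): the only exchange between hospitals for which consent is sought is between the two study centres. No request for outside records is described.

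None of these closes the gap.

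**Step 3: direction of the error.** Events known only to an outside hospital can be lost, and the plan has no offsetting route by which false events are added. The bias is therefore downward.

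**Step 4: the window.** Section 8.3 counts complications to 3 months after discharge in one sentence and to 3 months after baseline in another. Suppose an inpatient is enrolled *d* days before discharge:
- T3 = baseline + 3 months.
- End of the discharge-based window = baseline + *d* days + 3 months.
- Difference = *d* days after T3.

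A questionnaire completed at T3 would miss the last *d* days of the discharge-based window. For participants enrolled as outpatients, whom Section 8.3 allows for, a discharge date may not exist at all. Adding a question without settling the window would leave part of the gap open.

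**The case against.** The asymmetry can be defended. A patient can say whether an admission took place. A complication, as Section 8.3 defines it, requires a clinical judgement: harm in the course of or after specialist care, serious enough to force a change of treatment or leave permanent damage. Medical records are a normal source for that judgement, and events treated only by a general practitioner or at home may not meet the definition. This stands as a limit on the fix. It argues for having the study team judge reported events against the definition, not for leaving outside events unsought.

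It can also be said that outside events are not certain to be lost. A confirmed outside re-admission alerts the researcher, letters may reach the study hospital's file, and the second statement refers to medical records in general. That is fair, and the accurate wording is that such events can go unrecorded. The protocol makes none of these routes a procedure.

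A reader might infer more than the document supports:
- **That complications are the only structured record of harm after discharge.** Re-admissions and mortality are also structured, and adverse events are recorded when reported or observed.
- **That the undercount distorts the planning of the later trial.** Section 3 bases feasibility of the subpopulations on recruitment, drop-out, adherence and study measurements, and the later sample size on protein and energy intake. No section uses complication rates for either.
- **That the comparison between products is biased.** Nothing suggests that outside care depends on the product, and randomisation is stratified by site and patient population (Section 8.2), which should roughly balance differences in capture along those lines.

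**Conclusion.** The inconsistency is real and lies within a single paragraph. Followed as written, the plan can count an outside re-admission and miss the complication behind it, so the complication outcome is biased downward and need not agree with the re-admission outcome.

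The size cannot be stated. It depends on how many complications occur after discharge, what share is treated outside the two study hospitals, and how often those events still reach the study record. The protocol gives none of these, and any figure would be pure assumption. Complications during the stay at a study hospital are not affected.

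The conclusion assumes only that some participants receive specialist care elsewhere during follow-up, which the protocol's own reason for the questionnaire already accepts. Because this is a secondary outcome in a pilot whose primary endpoint is feasibility, the point does not threaten the main conclusions. It is worth correcting because the remedy is cheap.

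**What to change.** 1. In the questionnaire that already confirms re-admissions, add a question on the reason for any outside admission and one on any complication treated by a specialist elsewhere.
2. Have the study team judge each reported event against the Section 8.3 definition, count only those that meet it, and code them in the same four categories.
3. Record the source of each complication (EPR or participant) in the Castor database, and report the EPR-only rate and the combined rate side by side.
4. Reconcile the two complication windows in Section 8.3, state how the window applies to participants enrolled as outpatients, and time the questionnaire so that it covers the whole of the chosen window.

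The cost is one or two items on an existing questionnaire, one database field and a short text correction. If the discharge-based window is kept, a brief contact after T3 would also be needed for participants enrolled before discharge. The downside is that participant-reported events are less well documented than those in the record. The source field makes that visible, and the EPR-only rate remains available.

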#### *Qualitative interviews at T3*

All participants of the pilot feasibility study will be approached by the researcher for an in-depth interview. Patients will be interviewed using a topic list. The topic list is based on the subscale 'Quality' of the validated 'measure of food access in hospitals' questionnaire (28), adapted to the use of ONS, and complemented with additional questions about sustainability. These interviews will be conducted using purposeful sampling based on sex, age, and patient group. We will continue these interviews till data saturation (no new information emerges) is reached. The estimated time for this interview will be set at 45 minutes.

## **8.4 Withdrawal of individual research participants**

Participants can leave the study at any time for any reason without any consequences if they wish to do so. The investigator can decide to withdraw a participant from the study for urgent medical reasons.

### **8.4.1 Specific criteria for withdrawal (if applicable)**

Not applicable

## **8.5 Replacement of individual research participants after withdrawal**

In this pilot feasibility study, participants will not be replaced after withdrawal, as both recruitment and drop-out rates are key measurements of feasibility.

## **8.6 Follow-up of research participants withdrawn from treatment**

Not applicable

## **8.7 Premature termination of the study**

In case the study is terminated prematurely, the investigators will notify the CCMO and the local ethical committee within 15 days, including the reasons for premature termination. Premature termination of the study is possible if the sponsor (i.e. Radboudumc), the government or the judging medical ethical committee (METC Radboudumc) decides to end the study. This could be decided when the study has led to unsafe or unethical situations.

# **9. SAFETY REPORTING**

## **9.1 Temporary halt for reasons of research participant safety**

In accordance to section 10, subsection 4, of the WMO, the sponsor will suspend the study if there is sufficient ground that continuation of the study will jeopardise participant health or safety. The sponsor will notify the review committee without undue delay of a temporary halt including the reason for such an action. The study will be suspended pending a further positive decision by the review committee. The investigator will take care that all participants are kept informed.

## **9.2 AEs, SAEs**

### **9.2.1 Adverse events (AEs)**

Adverse events are defined as any undesirable experience occurring to a participant during the study, whether or not considered related to oral nutritional supplements intervention or study procedures. All adverse events reported spontaneously by the participant or observed by the investigator or his staff will be recorded.

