**3. STUDY DESIGN**

This study is a pilot randomized feasibility study in patients with cancer and lung diseases, cardiology patients, patients with cardiothoracic surgery, and orthopaedic patients at risk for inadequate nutritional intake to evaluate feasibility and patient satisfaction necessary to determine a suitable patient population and calculate the sample size for a larger RNIT (i.e. study 2). In study 2, a large RNIT will be conducted to establish the long-term efficacy of plant-based vs animal-based ONS. During this pilot study, patients who are advised ONS according to usual care and signed informed consent (IC) will be randomized to receive either plant-based ONS or animal-based ONS. Several measurements will be performed at 0 and 3 months. A total of 60 patients will be included. The main aim is to establish the feasibility in terms of recruitment, drop-out rate, adherence, and study measurements of the different subpopulations, reflecting feasibility for performing study 2. Furthermore, we will collect data on protein and energy intake, which will be used for the sample size calculation of study 2. Apart from the quantitative measurements, study 1 will also be setup as a qualitative study to determine patients' satisfaction, wishes and needs towards the ONS. Data on patients' satisfaction will only be used as observational data, no comparison between the two types of products will be made.

Measurements will be performed during hospital admission, or before/after an already scheduled appointment at the hospital outpatient clinic (baseline T0), and three months after baseline (T3). Within these 3 months, patients will be contacted by the researcher 1 month after the start (T1) and 2 months after the start (T2) for a 'check-in' conversation. For this conversation the researcher will either make a phone call or have brief conversation at the

hospital if the patient is already there for another appointment. The researcher will ask about any changes in body weight, discuss changes in the nutritional advice provided by the dietitian, ensure the patient is still correctly filling out the logbook, and address any questions or concerns related to the study. The study will be conducted at Radboud university medical center (Radboudumc) in Nijmegen, the Netherlands, and Maastricht University Medical Center (Maastricht UMC+) in Maastricht, the Netherlands.

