### **6.3 Summary of findings from clinical studies**

Not applicable, no previous studies with this plant-based ONS have been performed before.

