#### e. Analysis of potential effect

No potential adverse effects are known for the use of ONS.

f. Pharmacokinetic considerations

Not applicable

g. Study population

Patients from the oncology, lung diseases, cardiology, cardiothoracic surgery, and orthopaedic departments at risk for inadequate nutritional intake, age  $\geq 18$  years, treated at Maastricht UMC+ and Radboudumc.

h. Interaction with other products

No interactions have been reported.

i. Predictability of effect

High predictability of effect has been reported from earlier intervention studies mentioned above with regard to the use of ONS in patients at risk of malnutrition.

j. Can effects be managed?

Strict inclusion and exclusion criteria have been set for the inclusion of participants. The experimental trials will be performed at the nursing ward or in the clinical research unit, dependent on the mobility of the participant. During measurements, a researcher will always be present. The strict guidelines on how to respond in case of emergency within the nursing wards of the hospital will be followed.

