## 13.2 Synthesis

The overall risk of participation in this study is negligible for patients. Consuming dairy products will form risks for people suffering from lactose intolerance, and consuming soy products will form risks for people suffering from soy allergy / intolerance. Therefore, these people will be excluded from participating in this study. Both types of ONS are medically available and are therefore safe for human consumption. All measuring procedures are completely safe and routinely being performed within the Radboudumc and Maastricht UMC+.

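### Milder intolerance of the supplement at home is captured only if the patient volunteers it, because no tolerance question is listed for T1, T2 or T3

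*Protocol*

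**What the plan says.** Section 9.2.1 defines an adverse event broadly, as any undesirable experience whether or not it is related to the product. It then fixes how events reach the record: "All adverse events reported spontaneously by the participant or observed by the investigator or his staff will be recorded".

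Between baseline (T0) and three months (T3) there are two planned contacts, T1 and T2. The Summary and section 11.4 put each at about 10 minutes, by phone or at a hospital visit. Their content is described twice:

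- Section 3: "The researcher will ask about any changes in body weight, discuss changes in the nutritional advice provided by the dietitian", followed by a logbook check and an invitation to raise questions or concerns.
- Section 8.3: the same list with one addition, "their satisfaction about the ONS, ensure the patient is still correctly filling out the logbook, and address any questions or concerns related to the study".

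Table 1 (section 8.3) has ten rows, and none is for adverse events or tolerance. It marks satisfaction at T3 only. The logbook is described as recording daily ONS amounts (section 8.3) and the current advice (section 6.6).

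Under adherence, section 2 asks for the percentage of ONS consumed against advised and for the reasons questionnaires were not completed. It does not ask why ONS was not consumed. Section 8.2 states that patients cannot be blinded.

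**The concern.** A rule that relies on volunteering or observation works on a ward. It works less well at home, where nobody is observing and a patient may regard nausea, bloating or loose stools as part of the illness or not worth mentioning.

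Two things are at stake. First, adherence is one of the four components of the primary endpoint. If intolerance is not asked about, a low percentage consumed cannot be separated into patients who could not tolerate the product and patients who disliked it, forgot it or no longer needed it. The planned non-inferiority trial would need that distinction. Second, patients know which product they have. Willingness to mention a symptom, or to blame the drink for it, may then differ between groups for reasons other than true tolerance.

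**Working it through.** The point concerns how data are collected and disputes no stated figure. The sample size of 60 (2 × 30) is a convenience sample and does not enter the argument. The check is to take each channel through which a mild symptom at home could reach the record.

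1. **Adverse-event rule (9.2.1).** Volunteered or observed only. Nothing is asked.

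2. **T1 and T2 check-ins (3 and 8.3).** Two contacts of about 10 minutes give 2 × 10 = 20 minutes of planned contact between T0 and T3. Neither list has a symptom or tolerance item. Section 8.3 gives an indirect opening through satisfaction and concerns. Section 3 omits satisfaction, and Table 1 does not mark it at T1 or T2, so it is unclear whether that opening exists in every call.

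3. **T3 visit (8.3 and Table 1).** The PG-SGA and the EORTC questionnaire are repeated. Their items are not printed in the protocol, so whether they touch on symptoms cannot be settled from it. They are scheduled as nutritional status and quality of life at T0 and T3, and no text carries their answers into adverse-event recording.

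4. **T3 interview (8.3 and 10.2).** The satisfaction topics named are taste, smell and satiety. Interviews use purposeful sampling and stop at saturation, so they need not reach every participant.

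5. **Complications (8.3).** These come from medical records without the patient volunteering them. The definition requires harm serious enough to change medical treatment or leave irreversible damage. Mild gastrointestinal symptoms would usually fall below it.

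6. **Readmission and mortality (8.3).** Collected from the patient record and confirmed by questionnaire. They do not detect mild symptoms.

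7. **Drop-out reasons (2).** These catch intolerance that makes someone leave and is given as the reason. Section 11.2 lets participants leave without giving one. Patients who stay and drink less are not covered.

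8. **Logbook (6.6 and 8.3).** Shows that intake fell, not why.

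No channel asks every participant, in the same words, whether the product caused trouble.

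The direction of the error follows from simple notation. Let n = 30 per group, p the true share with mild intolerance, and c the share of those cases that reach the record. Expected recorded cases are n × p × c, against a true n × p. Any c below 1 lowers the recorded rate by the factor c. If p is equal in both groups, the ratio of expected recorded cases is c(plant) / c(animal), which differs from 1 whenever reporting differs between the unblinded groups. The document gives n but neither p nor c, so only the direction can be stated.

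**The case against.** The strongest reply is that this is a coherent choice for two foods already in hospital use (sections 6.4 and 13.1 b), in a 60-patient feasibility study where tolerance is neither a primary nor a secondary endpoint. The researcher invites concerns at T1 and T2, section 8.3 adds satisfaction, and a complaint raised then can be recorded under the broad definition in 9.2.1. This limits the point to an improvement in method. It does not remove it: an invitation to raise concerns still depends on volunteering, and adherence is part of the primary endpoint.

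A reader might infer more than the document supports:

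- *That harms in general go unmeasured.* They do not. Complications, readmission, mortality and drop-out reasons are all collected, and quality of life is measured at T0 and T3.
- *That the risk statements contradict each other.* Section 13.1 e says "No potential adverse effects are known for the use of ONS" and section 6.3 says "no previous studies with this plant-based ONS have been performed before". Nothing known and nothing studied can both be true. Section 13.2 says that "consuming soy products will form risks for people suffering from soy allergy / intolerance", but excludes those people, so 13.1 e is loosely worded rather than refuted. Section 6.3 must also be read beside 13.1 b, which cites one study of a different plant-based ONS reported as tolerated and safe.
- *That a particular number of cases will be lost.* Any such number would rest on an assumed symptom rate and an assumed reporting rate, neither of which has a source in the document.
- *That a low count will be taken into the next trial as proof of safety.* Section 3 names feasibility, satisfaction and intake data as what passes forward. It does not name adverse-event counts.

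**Conclusion.** The point holds in a limited form. Non-serious intolerance at home is captured only passively. Milder symptoms that cause no complication, readmission or drop-out are likely to be under-counted, possibly unequally between groups, and tolerance-related reasons for low adherence may be missed. The size cannot be derived from the document. The conclusion rests on two assumptions: that some patients with mild symptoms do not mention them unless asked, and that the check-ins follow the content listed for them. It does not imply that either product is harmful. This is a modest weakness, worth correcting because the correction is cheap and serves the primary endpoint. Separately, sections 3 and 8.3 and Table 1 disagree on whether satisfaction is asked at T1 and T2, and that needs reconciling in any case.

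**What to change.** 1. In section 9.2.1, change the rule to solicited plus spontaneous collection.
2. Add one short adverse-event and tolerance question to the existing T1, T2 and T3 contacts, worded identically in both groups. Have it also ask whether any symptom was a reason for drinking less than advised.
3. Add a matching row to Table 1, marked at T1, T2 and T3.
4. Under adherence in section 2, add a sub-question on reasons for ONS not consumed.
5. Make section 3, section 8.3 and Table 1 agree on the check-in content, including whether satisfaction is asked at T1 and T2.

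Cost: no new visits or staff. At an estimated two minutes per contact, 2 × 3 = 6 minutes per participant, and at most 6 × 60 = 360 minutes (6 hours) across the study, plus a short data-entry form. The downside is that more minor symptoms due to the underlying disease will be recorded. Identical wording in both groups should keep that extra recording comparable, although it cannot remove the effect of patients knowing their product.
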